## **5.4 Intracerebral Microdialysis (Dose Level 4 Patients Only)**

.

### **5.4.1 Cycle 1 Day 1: Placement of the microdialysis catheters**

Before a catheter is placed into brain it will be flushed with artificial CSF. The catheter will be tunneled subcutaneously and then inserted into the brain tissue adjacent to the tumor resection margin. If feasible, a second catheter will be added. The wound will then be closed in standard fashion, anchoring the catheter to the scalp with suture and sterile dressings.

#### **5.4.1.1 Patients who undergo a craniotomy for tumor removal**

Once the study neurosurgeon has finished resecting as much tumor as safely possible, he will insert a 70 Brain MD Catheter (membrane length 10 mm; shaft length 100 mm, ref. no. P000050, M Dialysis, Solna, Sweden) in residual tumor or within 5-15 mm of the resection cavity. If feasible a second catheter will be added to a different geographic location.

The NSCs will then be injected. **At the margin of the catheter location, 2-4 of the 100-150  $\mu$ l aliquots of NSCs will be injected.** The total dose of NSCs, ( $1.5 \times 10^8$ )—will be administered as per section 5.2.2.1.

After the NSCs have been administered, a Rickham will be placed in residual tumor or peritumoral tissue to deliver subsequent doses of NSCs.

#### **5.4.1.2 Patients who undergo a stereotactic brain biopsy**

After performing the tumor biopsy, a 70 Brain MD Catheter will be passively introduced into the injection site through the biopsy track. If feasible, a second MD catheter will be added to a different geographic location. The study neurosurgeon will then place the Rickham through the same biopsy track, and the dose of NSCs ( $1.5 \times 10^8$ ) will then be administered through the Rickham catheter as per section 5.2.2.2

### **5.4.2 Cycle 1 Day 1: Radiographic confirmation of catheter position**

A CT scan without contrast will be obtained as soon as possible post-operatively to determine if the microdialysis catheter was placed correctly.

If the CT scan shows poor positioning of a catheter, such as placement in a ventricle or within the surgical cavity but not in brain tissue, it will be removed.

#### **5.4.3 Cycle 1 Day 1: Microdialysis setup**

Once the CT scan confirms correct placement of the microdialysis catheter, the inlet tubing of the catheter will be connected to a 2.5 mL syringe (106 Pump Syringe, ref. no. 8010191, M Dialysis, Solna, Sweden) filled with sterile artificial CSF (Perfusion Fluid CNS). The syringe will be placed in a portable syringe pump (107 MD Pump, ref. no. P000127, M Dialysis, Solna, Sweden). The flow control on the pump will be set at **1 $\mu$ L/min**, and the pump will be turned on. A plastic microvial (Ref. No. P000001, M Dialysis, Solna, Sweden) will be placed in the vial holder at the end of the outlet tubing to collect dialysate. This microvial can hold up to 200  $\mu$ l of fluid. It will need to be replaced with a new one every 3 hours.

When ready to leave the post-anesthesia care unit, the patient will be transferred to the Intensive Care Unit and stay there as long as the microdialysis catheter remains functional in order to monitor the microdialysis pump and collect the dialysate samples as outlined in sections 5.4.1.4.1 and 9.3.1.

Prophylactic antibiotic use will continue as long as the microdialysis catheter remains in place.

#### **5.4.4 Cycle 1 Days 4-10: Collection of dialysate and blood samples for measurement of intracerebral and plasma levels of 5-FC, leucovorin, and 5-FU.**

With patients who undergo intracerebral microdialysis, the first dose of 5-FC/leucovorin will be administered at 6 am on day 4 and continue every 6 hours for the 7 day dosing period.

##### **5.4.4.1 Collection of dialysate samples**

On day 4, just prior to the first dose of 5-FC/leucovorin, a new microvial will be placed in the holder of the outlet tubing of the microdialysis catheter. The microvial will be changed to a new one **every 60 minutes for the next 24 hours**, and thereafter the microvial will be switched every 3 hours until the patient has completed the 7 day course of 5-FC/leucovorin. Please see section 9.2.1 for further details about collection of the dialysate samples.

The patient will remain hospitalized for as long as the microdialysis catheter is in place. During the period of dialysate collection, a patient may be mobile within the confines of the collection system. For example, s/he may move from bed to chair or commode and so on.

If the catheter stops functioning and is removed before the patient has completed the 7-day course of 5-FC/leucovorin, then s/he can be discharged from the hospital and finish taking 5-FC/leucovorin as an outpatient.

##### **5.4.4.2 Removal of the microdialysis catheter**

Approximately 6 hours after the last dose of 5-FC has been administered, the microdialysis catheter will be removed percutaneously at the bedside. Xylocaine for local anesthesia will be used as needed. The entry site of the catheter will be closed with a suture or steri-strips as necessary and a clean dressing applied.

##### **5.4.4.3 Collection of plasma samples.**

During collection of the dialysate samples, blood samples will be drawn in order to compare systemic and intracerebral levels of 5-FC, leucovorin, and 5-FU.

Pharmacokinetic (PK) sampling will be performed before and after 5-FC and leucovorin have reached steady-state.

**On days 4 and 5**, blood samples will be drawn just prior to the 6 am dose of 5-FC/leucovorin and then every 30 minutes during the first 3 hours after that dose is taken by the patient. Additional blood samples will be obtained 4 hours after the 6 am dose and then just prior to the next dose at noon.

**On days 6, 7, and 8**, blood samples will be obtained just before the 6 am dose of 5-FC/leucovorin and then 90 minutes later.

Please see section 9.2.2 for further details about collection of the PK blood samples.

If the microdialysis catheter becomes non-functional, then blood draws for plasma PKs will stop.

## 5.5 Definition of Dose-Limiting Toxicity (DLT)

Toxicities will be graded according to the NCI Common Terminology Criteria for Adverse Events version 4.0. **All patients receiving any number of NSCs will be evaluated for dose limiting toxicity criteria.**

**A DLT is defined as an adverse event that:**

- (a) is related to the administration of NSCs, 5-FC, or leucovorin, or any combination of the agents, with an attribution of possible, probable, or definite, and
- (b) occurs during the first treatment cycle (including Cycle 2 Day 1 safety assessments), and
- (c) meets any of the following criteria:

### Discontinuation toxicities

1. Receives less than 80% of study treatments due to a toxicity related to NSCs, 5-FC, or leucovorin, except CNS toxicities that are present at baseline or attributable to the location of the tumor or the neurosurgery.

### Hematological toxicities

1. Grade 4 thrombocytopenia
2. Grade 4 neutropenia lasting > 7 days
3. Grade 4 anemia
4. Febrile neutropenia if ANC < 0.5 x 10^9/L

### Nervous system disorders

5. Grade 3 CNS disorder lasting > 7 days that is not present at baseline and is not attributable to the location of the tumor or the neurosurgery.
6. Second occurrence of a grade 3 CNS disorder that is not present at baseline and is not attributable to the location of the tumor or the neurosurgery.
7. Any grade 4 CNS disorder that is not present at baseline and is not attributable to the location of the tumor or the neurosurgery.

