### Non-hematological, non-nervous system toxicities

8. Grade 3 toxicity despite maximal medical therapy lasting > 7 days.
9. Grade 3 toxicity resulting in study agent discontinuation (permanently removed from study treatment).
10. Grade 4 toxicity, except grade 4 diarrhea that responds to maximal medical therapy within 3 days.

Please note: An allergic reaction to the NSCs is excluded from the DLT definition, because NSC dose reduction is not appropriate in this situation. The possible occurrence of allergic reactions to the NSCs is addressed by the study stopping rules (Section 5.9).

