### 6.2.3 Chemotherapy toxicities

#### 6.2.3.1 5-FC

**Per the package insert for systemic 5-FC, the expected toxicities for 5-FC are:**

*Cardiovascular:* Cardiac arrest, myocardial toxicity, ventricular dysfunction.

*Ear and labyrinth disorders:* vertigo, hearing loss.

*Endocrine & metabolic:* Hypoglycemia, hypokalemia.

*Gastrointestinal:* Nausea\*, vomiting\*, abdominal pain\*, diarrhea\*, anorexia, dry mouth, duodenal ulcer, gastrointestinal hemorrhage, ulcerative colitis, enterocolitis\*.

*Hematologic:* Anemia, agranulocytosis, aplastic anemia, eosinophilia, leukopenia, pancytopenia, thrombocytopenia, and bone marrow aplasia including fatal cases.

*Hepatic:* Acute hepatic injury including hepatic necrosis with possible fatal outcome in debilitated patients, hepatic dysfunction, jaundice, bilirubin elevation, increased hepatic enzymes.

*Immune system disorders:* Allergic reaction.

*Nervous system disorders:* Ataxia, headache\*, paresthesia, parkinsonism, peripheral neuropathy, sedation, convulsions/seizure.

*Psychiatric:* Confusion\*, hallucinations\*, psychosis.

*Renal and urinary:* Azotemia, BUN elevation, crystalluria, renal failure, creatinine elevation.

*Respiratory:* Respiratory arrest, chest pain, dyspnea.

*Skin and subcutaneous tissue disorders:* Rash, pruritus, urticaria, photosensitivity, Lyell's syndrome (toxic epidermal necrolysis).

*Miscellaneous:* Fatigue, weakness, fever/pyrexia.

\*An asterisk signifies a common event according to Micromedex (updated July 2014).

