Vomiting or Nausea Grade 3, despite maximal medical management		Hold study treatment until resolution to ≤ grade 1  For patients not taking leucovorin First event: resume treatment at pre-hold dose. Additional events: restart treatment with a 25% decrease in 5-FC from the pre-hold dose.  For patients taking leucovorin First event: resume treatment at pre-hold dose. Second event: resume treatment at the same dose of NSCs and 5-FC, but permanently discontinue leucovorin. Additional events: resume treatment with a 25% dose reduction of 5-FC of the pre-hold dose.
Vomiting Grade 4, despite maximal medical management		Hold study treatment until resolution to ≤ grade 1  For patients not taking leucovorin Restart treatment with a 25% decrease in 5-FC from the pre-hold dose.  For patients taking leucovorin First event: resume treatment at the same dose of NSCs and 5-FC, but permanently discontinue leucovorin. Additional events: resume treatment with a 25% dose reduction of 5-FC of the pre-hold dose.
Nervous System Disorders		
Grade 3 Nervous System Disorder that is not attributable to tumor location or neurosurgery and is considered a least possibly attributable to NSCs, 5-FC, or leucovorin, or any combination and is not an immune response to study agents.	NSCs, 5-FC, leucovorin	Hold treatment until resolution to ≤ grade 1.  First event: If resolves within 7 days, resume treatment at pre-hold dose.  If does not resolve within 7 days, resume treatment with a dose reduction of NSCs and 5-FC by 25% of the pre-hold dose. If the patient is taking leucovorin, discontinue leucovorin.*  Second event: Resume treatment with dose reduction of NSCs and 5-FC by 25% of the pre-hold dose. If the patient is still taking leucovorin, discontinue leucovorin.*  *If the temporal association implicates NSCs or 5-FC (and leucovorin) rather than both/all agents, dose reductions may apply only to the implicated agent.

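### Read literally, section 5.5 has no grade-based DLT item for peripheral nerve toxicity, so a severe event late in cycle 1 can be scored as no DLT

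*Combined protocol and SAP*

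**What the plan says.** Section 5.5 counts an adverse event as a DLT if it is at least possibly related to a study agent, occurs in cycle 1 (up to and including the cycle 2 day 1 safety assessments), and meets one of the listed criteria. The criteria fall into four blocks.

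- **Discontinuation**, which depends on neither grade nor organ: "Receives less than 80% of study treatments due to a toxicity related to NSCs, 5-FC, or leucovorin". The exception attached to it covers only certain CNS toxicities.
- **Hematological**, items 1-4.
- **Nervous system disorders**, items 5-7: "Grade 3 CNS disorder lasting > 7 days that is not present at baseline", "Second occurrence of a grade 3 CNS disorder that is not present at baseline" and "Any grade 4 CNS disorder that is not present at baseline". Each also excludes events explained by tumor location or the neurosurgery.
- **The remaining group**, items 8-10, headed "Non-hematological, non-nervous system toxicities".

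Section 6.2.3.1 lists the expected 5-FC toxicities from the package insert. Its nervous system entry includes "paresthesia, parkinsonism, peripheral neuropathy, sedation, convulsions/seizure". Table 6.3.4, which governs holds and dose changes, uses the wider term: its row begins "Grade 3 Nervous System Disorder that is", and a matching row covers grade 4.

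**The concern.** A peripheral nerve disorder belongs to the nervous system but not to the CNS. On the literal wording, items 5-7 do not reach it and items 8-10 exclude it. Table 6.3.4 would nevertheless hold treatment for the same event at grade 3 or 4. An event serious enough to stop dosing therefore need not be a DLT, although the same grade 4 event in the CNS would count under item 7. In another non-hematological organ it would count under item 10, apart from the exceptions for responsive diarrhea and for allergy to the cells.

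The DLT count drives the 3+3 decisions and the MTD definition in section 5.6. It also feeds the first stopping rule in section 5.9 and the DLT rate with 90% limits in section 13.3.4. In cohorts of three or six, a single event scored differently changes the decision.

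**Working it through.** **The plan's own figures.** Section 13.1 says that six patients show a toxicity with a true rate of 0.25 in about 82% of trials: 1 - 0.75^6 = 0.822. It also gives a maximum 90% margin of 0.35; the exact (Clopper-Pearson) half-width at 3/6 is 0.347. Both reproduce, and neither is in dispute.

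**Step 1: which DLT items reach a related grade 4 peripheral neuropathy?**

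| Section 5.5 block | Reaches it? |
|---|---|
| Discontinuation | Only if under 80% of treatment is received because of it |
| Items 1-4, hematological | No |
| Items 5-7 | No: CNS only |
| Items 8-10 | No: nervous system excluded |

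The discontinuation item is the only route.

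**Step 2: when does that route close?** Inputs are 5-FC every 6 hours on days 4-10 and 18-24 (section 5.7) and cell doses on days 1 and 15. I assume four doses on each dosing day.

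- Doses per course: 7 x 4 = 28. Per cycle: 2 x 28 = 56.
- Pooled over the cycle: 0.80 x 56 = 44.8, so 45 doses are needed. 45 - 28 = 17 in the second course. Days 18-21 supply 16, so the 17th falls on day 22.
- Stopping after day 21: (28 + 16)/56 = 44/56 = 78.6%, a DLT.
- Stopping after day 22: (28 + 20)/56 = 48/56 = 85.7%, not a DLT.
- Counted per course: 0.80 x 28 = 22.4, so 23 doses are needed. Days 18-22 supply 20, so the 23rd falls on day 23.

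Section 5.5 does not say which denominator applies, so the boundary is day 22 or day 23. Both cell doses have normally been given by then. From that point to cycle 2 day 1, a related grade 4 peripheral event meets no DLT item. Under section 5.6 the patient has received enough treatment to be counted for dose escalation and, once followed through the cycle 2 day 1 assessments, enters the cohort as a patient without a DLT.

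**Step 3: effect on the 3+3 decision.** At 0/3 the trial escalates; at 1/3 it adds three patients. At 1/6 it escalates; at 2/6 the MTD has been exceeded.

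The documents give no rate for such events, so the rates below are assumptions, with independent patients and no other DLTs. With counted DLT probability p and q = 1 - p, the chance of escalating past a level is q^3 + 3pq^2 x q^3. At p = 0.25 this is 0.422 + 0.178 = 0.600.

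| Assumed true rate | All counted | Half counted | None counted |
|---|---|---|---|
| 10% | 0.91 | 0.97 | 1.00 |
| 25% | 0.60 | 0.86 | 1.00 |
| 33% | 0.43 | 0.78 | 1.00 |

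The last column is a bound, because the 80% item does catch earlier events that cost enough doses. The share that would start late is unknown.

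**The case against.** **The 80% item catches many of these events.** This stands. A reader might infer that severe peripheral neuropathy never counts and that escalation would always continue. The documents do not support that. A peripheral event that ends treatment before about day 22 is a DLT. So is one that costs the patient the day 15 cells and the second course, because under section 6.4.1 only about half the treatment is then received.

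**Events that start on days 11-14 and recover by day 22.** A reader might infer that these escape too, because section 6.4.1 allows the delayed second course in the same cycle. Table 6.3.4 does not support full dosing in that case. A grade 4 event leads to an MRI, then either discontinuation or restart at reduced dose. A grade 3 event lasting more than 7 days leads to a 25% reduction. If 5-FC is reduced, exposure is (28 + 0.75 x 28)/56 = 87.5% pooled, but 75% for the second course alone, so the outcome depends on the undefined denominator. A first grade 3 event resolving within 7 days is not a gap, since item 5 would not count it in the CNS either. The point therefore rests on late onset only.

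**CNS may be loose shorthand.** Items 5-7 stand under a heading that names the whole nervous system, and the next heading is its complement. That is a fair reading of intent. But the protocol never defines the term broadly, and the exclusions for tumor location and neurosurgery fit a literal CNS meaning. Two assessors could score the same event differently.

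**5-FC is not escalated.** Dose levels 1-3 share one 5-FC dose, so a missed systemic 5-FC event says little about the steps in cell number. This limits the impact. It matters more at level 1, where two DLTs trigger level -1, and at level 4, where leucovorin is added.

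**The event would still be seen.** All patients are followed for toxicity, the protocol management team decides escalation, and the phase II dose also rests on the toxicity profile. That is a safeguard, but it does not correct the DLT count or the reported DLT rate. Peripheral neuropathy is also not marked as common in section 6.2.3.1.

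**Conclusion.** The gap is real on the text, and narrow. A related grade 3-4 peripheral nerve toxicity meets no grade-based DLT item and counts only if it takes cycle 1 treatment below 80%. The clear case is a grade 4 event starting from about day 22-23 up to cycle 2 day 1, with at least 45 of 56 5-FC doses (pooled count) and both cell doses received. It can be scored as no DLT, and escalation can continue.

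The size is one event per decision. No expected frequency can be given, and the probabilities shown rest on assumed rates. The conclusion depends on reading CNS literally, on four 5-FC doses per dosing day, and on treatment having run to schedule until onset.

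**What to change.** Reconcile the terms in section 5.5 (items 5-7 and the heading of items 8-10) with each other and with Table 6.3.4. Every related non-hematological event, apart from the exclusions already stated, should fall into exactly one graded DLT group.

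Two wordings would do this: use the nervous system term throughout items 5-7, or make the heading of items 8-10 exclude only CNS toxicities. They are not equivalent. Items 5-7 count a second grade 3 occurrence and exclude events present at baseline or due to tumor location or surgery. Items 8-10 count a grade 3 event that causes permanent discontinuation. The sponsor should choose which group takes peripheral events and say so.

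The cost is a change of terms by amendment, with no change to dosing or to the 3+3 rules. The small downside is that a rare extra event could count as a DLT.

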### Non-hematological, non-nervous system toxicities

8. Grade 3 toxicity despite maximal medical therapy lasting > 7 days.
9. Grade 3 toxicity resulting in study agent discontinuation (permanently removed from study treatment).
10. Grade 4 toxicity, except grade 4 diarrhea that responds to maximal medical therapy within 3 days.

Please note: An allergic reaction to the NSCs is excluded from the DLT definition, because NSC dose reduction is not appropriate in this situation. The possible occurrence of allergic reactions to the NSCs is addressed by the study stopping rules (Section 5.9).

## 5.6 Study Design

The study will implement a standard 3+3 design. The goal will be to determine the maximum tolerated dose (MTD), which is defined as the highest dose level tested in which fewer than 33% of patients experienced a DLT attributable to the treatment regimen of NSCs with 5-FC and leucovorin, when at least 6 patients were treated at that dose and are evaluable for toxicity. If the MTD has not been reached with 1.5 x 108 NSCs, 37.5 mg/kg q6h 5-FC and 25 mg q6h leucovorin (dose level 3 plus leucovorin), then that dose will be termed the maximum feasible dose (MFD).

- 5.6.1** Phase I cohorts will be of 3 or 6 participants, as indicated by the dose-escalation criteria.
- 5.6.2** The dose schedule is provided in the table in section 5.7. The first cohort of patients will start at dose level 1.
- 5.6.3** Dose escalation will proceed through the identified doses without skipping any dose levels.
- 5.6.4** *Enrollment of the first 3 patients to dose levels 1-3 will be staggered* by requiring that each of the first 3 patients be separately observed for 4 weeks (or until the DLT assessment period has ended) before the next patient can start treatment on that dose level.
- 5.6.5**
- 5.6.6** Dose escalation rules:
  - 5.6.6.1 If 0/3 study participants experiences a DLT, the next cohort of 3 study patients will be treated at the next higher dose level.
  - 5.6.6.2 If 1/3 study participants experiences a DLT, the cohort will be expanded by another 3 study participants who will be treated at the same dose level for a total of 6 study participants.
  - 5.6.6.3 If 1/6 participants experiences a DLT, the next cohort of 3 study participants will be treated at the next higher dose level.
  - 5.6.6.4 If 2 or more participants of either a 3 participant or 6 participant cohort encounter a DLT, then the MTD has been exceeded. If applicable, three (more) participants will be enrolled at the next lower dose level.
  - 5.6.6.5 At least 6 patients will be treated at the MTD (or MFD, if the MTD is not reached).

For a patient to be counted for dose escalation, s/he must receive at least 80% (+/- 5%) of the assigned NSCs on days 1 and 15 and 80% (+/- 5%) of the 5-FC (and leucovorin, as indicated) on days 4-10 and 18-24 during cycle 1 and be followed up to and including cycle 2 day 1 safety assessments or have experienced a DLT.

All study patients enrolled are to be fully followed for toxicity; any study patients who are not evaluable for dose escalation will be replaced. Intra-patient dose escalation is not allowed.

Dose level 4 patients will undergo intracerebral microdialysis, along with collection of blood samples, for pharmacokinetic analysis in order to characterize the relationship between intracerebral and systemic concentrations of 5-FC and 5-FU at the MTD level, as well as to assess intracerebral concentrations of leucovorin.

## 5.7 Dose Escalation Schema

Dose Level	Neural Stem Cells (i.c. on days 1 & 15)	5-FC (mg/kg q 6h p.o. on days 4-10 & 18-24)	Leucovorin (mg q 6h p.o. on days 4-10 & 18-24)	Initial Enrollment	If 1 DLT, additional enrollment
------------	---	---	--	--------------------	---------------------------------

-1 a	$3.75 \times 10^7$	28	---	3	3
1	$5 \times 10^7$	37.5	---	3	3
2	$1 \times 10^8$	37.5	---	3	3
3	$1.5 \times 10^8$	37.5	---	3	3
4 b,c	Highest tolerated dose combination of 5-FC and NSCs		25	3	3

aIf a DLT is observed in 2 or more patients at dose level 1, then a de-escalation dose, **dose level -1** will be tested. With dose level -1, the doses of NSCs and 5-FC will both be reduced by 25%; however, if the DLT can clearly be attributed only to 5-FC, then only the dose of 5-FC will be reduced by 25% (likewise for the NSCs if the DLT is clearly attributable to only the NSCs) for dose level -1.

bIf the addition of leucovorin to the highest tolerated dose combination of 5-FC and NSC requires a dose de-escalation, then leucovorin will be discontinued and the MTD/MFD will be the highest tolerated dose combination of 5-FC and NSCs without leucovorin. A total of 6 patients will be treated at the maximum tolerated dose (MTD), or if the MTD is not reached, at the maximum feasible dose (MFD).

cPatients on dose level 4 will undergo intracerebral microdialysis to measure NSC-mediated conversion of 5-FC to 5-FU.

